4.8.1. AI man aged 50-75 years old

4.8.2. AI woman aged 21-75 years old

4.9. Inclusion Criteria for Aim 8 – Pilot Testing of the Interventions

4.9.1. For the Breast Cancer Intervention: AI women age 50-75, average risk for breast cancer, and never had a mammogram OR not had a mammogram within the past 2 years.

4.9.2. For the Colorectal Cancer Intervention: AI men and women aged 45-75, average risk for CR cancer, and never had a fecal occult blood test (FOBT), or fecal immunochemical test (FIT) or a colonoscopy OR not had a FOBT or FIT in the past year, OR no colonoscopy in the past 10 years.

4.9.3. For the Cervical Cancer Intervention: women aged 21-75, never had a cytology (Pap smear) OR had a Pap smear more than 3 years ago OR women aged 30-75, and never had screening with a combination of cytology and human papillomavirus testing OR no combination of testing in the past 5 years.

4.10. **Exclusion Criteria**

- 4.10.1. Cognitively impaired adults are excluded from participation
- 4.10.2. Adults not able to consent for themselves are excluded from participation
- 4.10.3. Prisoners may not participate in this study

5. Number of Subjects

5.1. Aim 3

- 5.1.1. Aim 3 is formative and therefore the sample size is not guided by a power analysis. For each of the up to 21 focus groups (until we reach thematic saturation), N=12-15 eligible persons will be invited, with the expectation that on average N=8-12 will attend. Since this is a community-based participatory study, we will not turn away any eligible person who show up for the focus group. Thus, we seek approval for including 150 AI men and women for the focus group.
 - 5.1.1.1. *Focus Groups Among Women aged 50-75 on Cancers of Breast, Colon-Rectum, and Cervix*: up to 5 Focus Groups, or until we reach thematic saturation (participants: N=60-75)
 - 5.1.1.2. *Focus Groups Among Men aged 50-75 on Cancers of the Colon-Rectum and Prostate*: up to 5 Focus Groups, or until we reach thematic saturation (participants: N=60-75)
 - 5.1.1.3. *Focus Groups Among Women aged 21-49 on Cervical Cancer*: up to 5 Focus Groups, or until we reach thematic saturation (participants: N=60-75)
 - 5.1.1.4. *Focus groups with Tribal Advisory Panel (TAP) members*: up to 3 Focus Groups, or until we reach thematic saturation (participants: N=36-45- total)
 - 5.1.1.5. *Healthcare Provider focus groups*: up to 3 Focus Groups, or until we reach thematic saturation (participants: N=36-45 total)

5.2. Aim 4

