- 5.2.1. Aim 4 is to conduct surveys with approximately N=250-280 eligible AI men and women.
 - 5.2.1.1. *Survey on Cancer of the Cervix (Women aged 21-49)*: N=50-60 AI women
 - 5.2.1.2. *Survey on Cancers of the Colon-Rectum, Breast, and Cervix (Women aged 50-75)*: N=100-110 AI women
 - 5.2.1.3. *Survey on Cancers of the Colon-Rectum and Prostate (Men aged 50-75)*: N=100-110 AI men

5.3. Aim 7

- 5.3.1. Aim 7 is to develop the interventions, including the small media, with about 12-15 TAP members (section 4.5) and 150 eligible AI men and women (we will invite 12-15 participants

in up to 15 total focus groups, with expectation that on average we will have 8-10 participants will attend) (section 4.8)

5.4. Aim 8

5.4.1. Aim 8 is to test the three interventions with about up to 150 eligible participants

Total between the Aims: N=706-850 participants

6. Study Timelines

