We will conduct up to 15 focus groups, up to 5 focus groups each among the following age/gender groups: Women aged 50-75, men aged 50-75, Women aged 21-49. The focus group interview guides are included as an appendix entitled “FocusGroupGuide(Women50-75)_2018_08_17_V1; FocusGroupGuide(Men50-75)_2018_08_17_V1; FocusGroupGuide(Women21-49)_2018_08_17_V1” and contains stem questions in the following areas: 1) knowledge about the respective cancer, 2) belief and attitudes regarding preventive behaviors in general, and cancer prevention in particular, 3) individual and social factors that facilitate and impede reducing risk and promoting better health, 4) factors that pose barriers obtaining screening exam, 5) factor that can facilitate obtaining a screening exam, and 6) strategies that can enhance screening behavior. We will invite 12-15 eligible persons for each of the focus groups and, with potential attrition, we anticipate about 8-12 persons per focus group. Before the discussion, participants will undergo informed consent using a consent letter requiring no documentation of written consent and we will obtain permission to digitally audio-record the session. We anticipate that each group session with women aged 21-49 will last about 90 minutes, and the group sessions with women and men aged 50-75 will last about 2 hours and we will digitally audio-record for subsequent transcription and analytic review. We will also collect baseline socio-demographic (age, sex, race/ethnicity, marital status, educational and employment status, health insurance coverage, primary language spoken at home, health literacy, and primary source of healthcare) information from each participant. See appendix entitled “Socio-DemographicSurvey(Zuni)_2019_02_11_V4”. Before starting the focus group, we will obtain written informed consent (see “ConsentForm_FocusGroupParticipation(Women-Men50-75)_2018_10_01_V2” and ConsentForm_FocusGroupParticipation(Women21-49)_2018_10_01_V2”). Following the discussion, women participating in the focus groups inquiring only about cancer of the cervix (Women Aged 21-49) will receive a \$50 merchandise card in appreciation of their time. Women and men participating in focus group inquiring about multiple cancers (i.e., the Women Aged 50-75 and Men Aged 50-75 groups) will receive a \$75 merchandise card in appreciation of their time. The slightly higher amount for the latter two groups is an acknowledgement of the additional discussion time that may be needed for these groups.

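### The Section 5 total of 706-850 is not the sum of its printed lines (814-910), has no stated counting basis, and rests on Aim 3 and panel figures that need reconciling

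*Combined protocol and SAP*

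**What the plan says.** Section 5.1.1 allows up to 21 Aim 3 focus groups and says of each that "N=12-15 eligible persons will be invited, with the expectation that on average N=8-12 will attend". It adds that "we will not turn away any eligible person who show up for the focus group" and then: "Thus, we seek approval for including 150 AI men and women for the focus group". The lines beneath give 60-75 participants for each of three community strata (five groups each), 36-45 for TAP groups and 36-45 for provider groups. The TAP line reads "up to 3 Focus Groups, or until we reach thematic saturation (participants: N=36-45- total".

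Section 5.2.1 gives 250-280 for Aim 4. Section 5.3.1 plans Aim 7 "with about 12-15 TAP members (section 4.5" and 150 community members, in up to 15 groups with 8-10 expected at each. Section 5.4.1 gives up to 150 for Aim 8. The section ends with "Total between the Aims: N=706-850 participants".

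Section 12 (Aim 3) repeats the community plan, "We will conduct up to 15 focus groups, up to 5 focus groups each among the following age/gender groups", and says that "with potential attrition, we anticipate about 8-12 persons per focus group". It invites 12-15 TAP members to each TAP group. Section 3 (community-based participatory research), Section 12 (Aim 1) and Section 30 give the Advisory Panel nine members.

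**The concern.** A total printed under a list should follow from the list, or the plan should say why it does not. Here it does not follow, and Section 5 gives both invited and attending numbers per group without saying which the Aim 3 lines or the total use. The Aim 3 approval number also stands directly above community lines that are larger than it, and the panel appears smaller than the groups to be drawn from it.

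These figures are the study's stated size and a number for which approval is sought. Section 12 (end of Aim 3) says that accrual is reported per participant to a national registry programme, so the unit of counting matters. Nothing inferential is at stake: Section 5.1.1 says that Aim 3 has no power analysis, and no analysis in Section 13 uses these counts.

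**Working it through.** **Printed lines (Sections 5.1 to 5.4)**

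- Aim 3: 3×60 + 36 + 36 = 252; 3×75 + 45 + 45 = 315
- Aim 4: 250; 280
- Aim 7: 12 + 150 = 162; 15 + 150 = 165
- Aim 8: 150; 150
- Sum: 252 + 250 + 162 + 150 = **814**; 315 + 280 + 165 + 150 = **910**

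Against 706-850 the differences are 814 − 706 = 108 and 910 − 850 = 60.

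**What the lines count.** For Aim 3, 5×12 = 60 and 5×15 = 75, and 3×12 = 36 and 3×15 = 45, so these lines are invitees. For Aim 7, 15×10 = 150, the upper expected attendance. The printed lines are therefore not on one basis.

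**Reproducing the stated total.** The one count found that matches both ends exactly is:

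- Low: 15×8 + 12 (TAP) + 12 (providers) + 250 + 12 (TAP, Aim 7) + 150 + 150 = **706**
- High: 15×15 + 15 + 15 + 280 + 15 + 150 + 150 = **850**

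This takes 8 attendees per community group at the low end and 15 invitees at the high end. It counts TAP members and providers once each, although 36-45 is printed for each. The plan does not state this count. Many combinations of its figures are possible, so this origin is an inference.

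**Single-basis totals from the plan's own figures**

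| Basis | Aim 3 | Aim 4 | Aim 7 | Aim 8 | Total |
|---|---|---|---|---|---|
| All invited | 252-315 | 250-280 | 192-240 | 150 | 844-985 |
| Expected session attendances | 168-252 | 250-280 | 132-165 | 150 | 700-847 |
| Expected persons per aim, TAP of 12-15 | 156-231 | 250-280 | 132-165 | 150 | 688-826 |
| Expected persons per aim, TAP of nine | 153-225 | 250-280 | 129-159 | 150 | 682-814 |

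The entries come from:

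- All invited, Aim 7: 12 + 15×12 = 192; 15 + 15×15 = 240.
- Session attendances: Aim 3 is 21×8 = 168 and 21×12 = 252. Aim 7 is 12 + 15×8 = 132 and 15 + 15×10 = 165.
- Persons, TAP counted once per aim and providers taken as different people in each group (3×8 = 24; 3×12 = 36): Aim 3 is 120 + 12 + 24 = 156 and 180 + 15 + 36 = 231.
- Persons, TAP of nine: Aim 3 is 120 + 9 + 24 = 153 and 180 + 9 + 36 = 225. Aim 7 is 9 + 120 = 129 and 9 + 150 = 159.

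**The Aim 3 approval number.** For the 15 community groups, 15×8 = 120, 15×10 = 150 and 15×12 = 180 are expected to attend, and 15×15 = 225 may be invited. For all 21 groups, expected attendance is 168-252.

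**Panel size.** Nine members fall 12 − 9 = 3 to 15 − 9 = 6 short of the invitees for one group. Over three sessions they give at most 3×9 = 27 attendances, against 36-45 listed.

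**The case against.** **The total.** A reader might infer a plain addition error of 108 and 60. The documents do not support that. The sum 814-910 is itself a mixture of invitees and attendees, so it is not the correct total and the differences do not measure the error. The stated total also lies within 1% of expected session attendances at each end (6/706 = 0.8%; 3/850 = 0.4%). This objection stands: the defect is an unstated and probably mixed basis. It does not rescue the total, because no single basis tabulated here gives 706-850.

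**The 150.** A reader might infer that 150 is below a planned 180. No passage plans 180 attendees. That figure is the top of expected attendance and also the low end of the invitee lines. The 150 is the exact midpoint of 120-180, and 15 groups is a ceiling, since recruitment stops at thematic saturation. This too stands. What remains is narrower: 150 leaves no room for the upper expectation while the plan turns nobody eligible away.

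**The panel.** A reader might infer a flat contradiction between nine and 12-15. The number nine is attached only to the Advisory Panel, and 12-15 only to the TAP. That they are one body is likely but not stated. Section 1 (Aim 1) and Section 12 (Aim 1) draw the TAP and the Advisory Panel from the same listed entities. Section 12 also gives the Panel (Aim 1) and the TAP (Aim 6a) the same task of setting priorities from Aims 4 and 5.

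**Timing.** Aim 3 fieldwork appears to be over. Section 12 reports about 140 completed surveys under Aim 4, for an instrument to be built on focus-group data, and describes post-intervention survey results under Aim 8 in the past tense. Raising a prospective ceiling may therefore be moot.

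**Conclusion.** The point holds as a minor error. The total of 706-850 is wrong as written: it is not the sum of its lines (814-910), and the plan states no counting basis. On persons enrolled per aim at expected attendance, the plan's figures give 688-826 or 682-814, depending on TAP size. Both assume that providers differ between groups.

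The other two parts are conditional. Read as covering the 15 community groups, the 150 suffices at an average of 10 per group but is 30 below upper expected attendance and 75 below the maximum invited (225 − 150). Read as covering all 21 groups, it is below even the minimum expected attendance of 168. If the Advisory Panel and the TAP are one body, nine members cannot supply the 12-15 invited per Aim 3 group, the 12-15 used in Aim 7, or the 36-45 listed.

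**What to change.** 1. Put every Section 5 line and the total on one labelled basis: persons enrolled per aim, summed over aims. Count TAP members once per aim. State that these are not unique persons across aims, because Section 20 recontacts Aim 4 participants for Aim 8 and TAP members recur in Aims 3 and 7. The total becomes 688-826 with a TAP of 12-15, or 682-814 with nine. If session attendances are preferred, label them so (700-847 on present figures).
2. State which groups the 150 covers. Where Aim 3 groups are complete, replace the planned figures with actual attendance. If any remain, set the approval number to cover the maximum invited for the groups it applies to.
3. Say whether the Advisory Panel and the TAP are one body. Reconcile the panel size across Section 3, Sections 5.1.1.4 and 5.3.1, Section 12 (Aims 1 and 3) and Section 30.

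The cost is text and number edits, with a possible IRB modification request if an approval number changes. No data collection or analysis is added.

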6.1. Aim 3 – Anticipated to occur over Year 1 of the study

6.1.1. Focus Groups: Participants will complete focus group activities anticipated to take about 2 hours for women and men aged 50-75, and about 60 minutes for women aged 21-49.

6.1.2. Focus Groups: Focus group activities with providers and Tribal Advisory Panel members anticipated to take about 45-60 minutes.

6.2. Aim 4 – Anticipated to occur over Year 2 of the study

6.2.1. Surveys: Participants will complete surveys anticipated to take up to 20 minutes for Men 50-75 years and Women 21-49 years, and 40 minutes for Women 50-75 years.

6.3. Aim 7 – Anticipated to occur over Year 3 of the study

6.3.1. Group discussion with TAP members 60 minutes

6.3.2. Focus Groups: Participants will complete focus group activities anticipated to take about 2 hours for women and men aged 50-75, and about 60 minutes for women aged 21-49.

6.4. Aim 8 – Anticipated to occur over Year 4-7 of the study

6.4.1. Baseline and 12 months post-intervention surveys: approximately 20-30 minutes each

6.4.2. Focus Groups or interviews: Participants will complete focus group activities anticipated to take up to 2 hours.

7. Study Endpoints

Endpoints for this study include completion of the 12-month post-intervention survey questionnaire by all eligible participants.

8. Research Setting

8.1. Patient Participant Recruitment

8.1.1. Participants will be recruited within the Zuni Pueblo community, working in community-based settings and with the IHS Zuni Comprehensive Health Center.

8.1.2. [name] and his study team staff will work closely with each of these participating groups towards recruitment of eligible participants. The research team will coordinate these activities with [name] and the CHRs. The behavioral study coordinator will communicate on a weekly basis with CHRs for purposive recruitment to the focus groups and interviews in Aims 3 and 7, and convenience sampling recruitment to the surveys in pilot testing of the interventions in Aim 8. A waiver of written consent will be requested for all participants.

8.1.3. Participants for the focus groups in Aims 3 and 7, and pilot testing of the intervention will be recruited through community-based settings in Zuni. We will use a combination of community meetings, health fairs, announcements and flyers placed in public places such as the Tribal Administration building, Zuni Health Initiative center, Community Center, Post Office, IHS Zuni Comprehensive Health Center. Tribal leaders will identify Tribal Advisory Panel members or consent to those nominated by peers based on experience and expertise. Participants for Aim 4 (survey) will be recruited by placing/ distributing flyers (see “RecruitmentFlyer_Survey_2020_09_02_V2”) to households selected from randomly identified streets in the Zuni Pueblo.

8.2. Provider Participant Recruitment

8.2.1. Provider participants for Aim 3 will be purposively recruited based on eligibility as a healthcare provider at the IHS Zuni Comprehensive Health Center.

8.3. Data Collection

8.3.1. The focus group sessions (Aims 3, 7, and 8) will be held at the Zuni Health Initiative’s center. The focus group with healthcare provider (Aim 3) will occur in a private conference room at the IHS Zuni Comprehensive Health Center. The participant surveys (Aim 4) will be interviewer-led and will be done over the phone. The intervention sessions and associated surveys (Aim 8) will be conducted at the Zuni Health Initiative’s center. The options will be provided to the participants so they can decide what the best is for them.

9. Resources Available

9.2.1. Not applicable

9.3. Other resources available to conduct the research

We have assembled an experienced research team led by [name] and assisted by [name] through the UNM Comprehensive Cancer Center's Behavioral Measurement and Population Science Shared Resource. Investigators have sufficient time and resources to complete the proposed study. All participating researchers have undergone updated human subjects training.

10. Prior Approvals

Upon departmental approval (from the UNM Comprehensive Cancer Center's PRMC), the departmental approval form is completed and uploaded to Click IRB under "supporting documents".

11. Multi-Site Research

N/A – UNM is the only site involved in this project.

12. Study Procedures

Aim 1: Develop a sustainable multi-directional, participatory collaboration (“community collaborative”) between the Zuni tribal leadership, Zuni stakeholders (i.e., Health and Wellness program directors and Community Health Representatives [CHRs], cancer survivors), IHS Zuni Comprehensive Health Center, Albuquerque Area Southwest Tribal Epidemiology Center (AASTEC), and the UNM Comprehensive Cancer Center (UNM CCC).

We will develop a participatory “community collaborative” between the Zuni tribal leadership, Zuni stakeholders and local organizations (i.e., Health and Wellness program directors, CHRs, cancer survivors), healthcare providers (i.e., IHS Zuni Comprehensive Health Center), a tribal non-profit organization (i.e., AASTEC), and UNM CCC to develop and implement a cancer prevention and control research agenda. The collaborative will ensure a non-hierarchical partnership model necessary for research with AIs. We will constitute a 9-member Advisory Panel, representing all the entities listed above. The Panel will meet bimonthly and actively participate to: define education and research needs for the community and clinic members, assist in developing qualitative data collection instruments, assist in documenting resources available for cancer prevention and control research, constituency check inferences based on the qualitative data, prioritize cancer prevention and control needs identified through data obtained through Aims 4 and 5, and develop a research agenda for evidence-based intervention research that address cancer health disparities in Zuni. We will (1) build on the various stakeholders’ strengths and integrate our respective knowledge and expertise, and (2) support an inter-dependent partnership, with a long-term commitment for mutually beneficial co-learning and capacity enhancement. Each member will receive a \$100 merchandise card per meeting for their participation on the Advisory Panel.

Aim 2: Empower and develop capacity (using the Freirean educational pedagogy for adult learning) among Zuni people to participate in relevant cancer control education and research.

We will educate and train all Zuni CHRs who express an interest about cancers of the breast, CR, cervix, and prostate. [name] from the Albuquerque Area Southwest Tribal Epidemiology Center (AASTEC) will lead the initial 3-day training. We will provide three 2-day refresher trainings every six months. The training modules will include: cancer (breast, CR, cervical, and prostate) among AIs; anatomy of the female breast and reproductive system, digestive system, male reproductive system; breast, CR, cervical, and prostate Cancer 101; screening guidelines; risk factors; and treatment and management approaches. The teaching approaches will include digital stories, PowerPoint presentations, anatomical models, vignettes, and narratives. Following the education and training regarding the four cancers, we will hire and train four (4) student CHRs in the conduct of qualitative research. We will train the CHRs in basic research methods including recruiting participants, facilitating focus groups, conducting semi-structured in-person interviews, analyzing qualitative in data analysis, and administering surveys. We will provide this training over 2 days. We will offer the Cancer 101 and research trainings at the Native Health Initiative’s office located in the Zuni Pueblo.

We will utilize principles of Freire’s empowerment pedagogy³⁷ to provide the education and training. The pedagogy provides a model to conduct education and nurture new skills by defining attributes of an ideal educational environment, the mode of effective education, and the incorporation of cultural and socio-ecological sensitivities within the educational context. The pedagogy, based on the problem posing method of learning, emphasizes dialogue and reciprocity. In this method, the educator ([name]) will present the CHRs with a particular situation as a problem to be solved by the group. It is anticipated that the CHRs will internalize and evaluate critically the information they receive in the course of participating in an open dialogue with the educator, i.e., interactive exchange of knowledge. In addition, they are invited to introduce into the educational setting current environment and life circumstances that affect, in this study, the risk for cancers of the breast, CR, cervix, and prostate; challenges for completing recommended screening tests. [name] will empower the CHRs to make the problem of avoiding cancer their own problem instead of his problem. Through this strategy, [name] will involve himself in an interactive process that allows him to gain more information about the beliefs and prevention issues for the four cancers while at the same time allowing the CHRs to be actively involved in a problem-solving process that leads to improved health.

Aim 3: Assess cancer control needs of the Zuni people regarding the screen detectable cancers and resources available at the Indian Health Service (IHS) Zuni Comprehensive Health Center to provide screening services.

We will conduct focus groups³⁸ with purposively sampled eligible participants. Eligible participants will include those who are not compliant with U.S. Preventive Services Task Force screening guidelines for the three cancers³⁹⁻⁴¹ and those who are eligible for prostate cancer screening. For breast cancer this would include AI women aged 50 to 74 at average risk for breast cancer who have never had a mammogram or have not had a mammogram within the past two years. For CR cancer, this would include men and women at average risk for CR cancer aged 50 to 74 and never had a fecal occult blood test (FOBT) or fecal immunochemical test (FIT) or a colonoscopy, or not had a FOBT or FIT test in the past year, or no colonoscopic exam in the past 10 years. For cervical cancer this would include women at average risk for cervical cancer aged 21 to 65 who have never had a cytology (Pap smear) or had a Pap smear more than 3 years ago; or women aged 30 to 65 who have never had screening with a combination of cytology and human papillomavirus (HPV) testing or no combination testing in the past five years. For prostate cancer, this would include men over the age of 50 years.

We will conduct up to 15 focus groups, up to 5 focus groups each among the following age/gender groups: Women aged 50-75, men aged 50-75, Women aged 21-49. The focus group interview guides are included as an appendix entitled “FocusGroupGuide(Women50-75)_2018_08_17_V1; FocusGroupGuide(Men50-75)_2018_08_17_V1; FocusGroupGuide(Women21-49)_2018_08_17_V1” and contains stem questions in the following areas: 1) knowledge about the respective cancer, 2) belief and attitudes regarding preventive behaviors in general, and cancer prevention in particular, 3) individual and social factors that facilitate and impede reducing risk and promoting better health, 4) factors that pose barriers obtaining screening exam, 5) factor that can facilitate obtaining a screening exam, and 6) strategies that can enhance screening behavior. We will invite 12-15 eligible persons for each of the focus groups and, with potential attrition, we anticipate about 8-12 persons per focus group. Before the discussion, participants will undergo informed consent using a consent letter requiring no documentation of written consent and we will obtain permission to digitally audio-record the session. We anticipate that each group session with women aged 21-49 will last about 90 minutes, and the group sessions with women and men aged 50-75 will last about 2 hours and we will digitally audio-record for subsequent transcription and analytic review. We will also collect baseline socio-demographic (age, sex, race/ethnicity, marital status, educational and employment status, health insurance coverage, primary language spoken at home, health literacy, and primary source of healthcare) information from each participant. See appendix entitled “Socio-DemographicSurvey(Zuni)_2019_02_11_V4”. Before starting the focus group, we will obtain written informed consent (see “ConsentForm_FocusGroupParticipation(Women-Men50-75)_2018_10_01_V2” and ConsentForm_FocusGroupParticipation(Women21-49)_2018_10_01_V2”). Following the discussion, women participating in the focus groups inquiring only about cancer of the cervix (Women Aged 21-49) will receive a \$50 merchandise card in appreciation of their time. Women and men participating in focus group inquiring about multiple cancers (i.e., the Women Aged 50-75 and Men Aged 50-75 groups) will receive a \$75 merchandise card in appreciation of their time. The slightly higher amount for the latter two groups is an acknowledgement of the additional discussion time that may be needed for these groups.

We will conduct up to 3 focus groups with members of the Tribal Advisory Panel (TAP). We will invite 12-15 eligible TAP members for each of the focus groups and, with potential attrition, we anticipate about 8-12 persons per focus group. The focus group will document individual, social, systemic, and cultural barriers/promoters to obtaining cancer screening services. We will also elicit their perspectives on evidence based strategies we can implement in Zuni that could potentially enhance cancer screening uptake (NOTE: We will submit a modification request for review and approval the Focus Group Guide

specifically developed for the TAP member focus group.). We will collect baseline socio-demographic information from the participants, using the instrument previously approved for use with providers (see below). Before starting the focus group, we will obtain written informed consent (see “ConsentForm_FocusGroupParticipation(TAPmembers)_2019_11_08_V2”) and permission to digitally audio-record the focus group. We anticipate the focus group to last 45-60 minutes. Following the discussion, the TAP members will receive a \$50 merchandize card in appreciation of their time or if federally employed, reimbursement for food and travel expenses.

We will conduct up to 3 focus groups³⁸ with purposively sampled eligible healthcare providers from the IHS Zuni Comprehensive Health Center. We will invite 12-15 eligible healthcare providers for each of the focus groups and, with potential attrition, we anticipate about 8-12 persons per focus group. The focus group will document resources available for providing cancer screening services, and structural and system-level promoters and barriers to providing screening. The focus group with the providers will also inquire about relevant MHOF constructs such as structural, social, cultural, and contextual influences on cancer screening. See appendix entitled “FocusGroupGuide(Provider)_2018_09_26_V1”. We will collect baseline socio-demographic information from the participants. See appendix entitled “Socio-DemographicSurvey(Providers-TAPmember)_2018_10_05_V2”. Before starting the focus group, we will obtain written informed consent (see “ConsentForm_FocusGroupParticipation(Provider)_2019_11_08_V2”) and permission to digitally audio-record the focus group. We anticipate the focus group to last 45-60 minutes. Following the discussion, the providers will receive a \$50 merchandize card in appreciation of their time or if federally employed, reimbursement for food and travel expenses.

We include month and year of birth (instead of age or full date of birth) and zip code in these demographics surveys because this is a Cancer Prevention study overseen by the Cancer Center’s DSMC and therefore required to provide limited accrual information to the NCI Clinical Trials Reporting Program (CTRP). The CTRP requires the following fields be provided per participant: Study ID, Zip Code, Country of Residence, Month of Birth, Year of Birth; Gender; Ethnicity; Race.

Aim 4: Evaluate the cancer-related knowledge, attitudes, and self-reported cancer screening practices using quantitative survey methods among a convenience sample of Zuni people.

We will use data from the focus group discussions to develop a survey instrument to document cancer-related knowledge, attitudes, self-reported cancer screening practices, and preferences for intervention strategies to enhance screening services (see “Survey_Men50-75_2020_06_22_V1”, “Survey_Women21-49_2020_06_2_V1”, and “Survey_Women50-75_2020_06_22_V1”). We will also collect socio-demographic (age, sex, race/ethnicity, marital status, educational and employment status, health insurance coverage, primary language spoken at home, health literacy, and primary source of healthcare) information. Unfortunately, the three surveys listed above did not have a question to determine age of the participants. To address this oversight, we have revised the 1-page Contact Sheet (see “ContactSheet_2021_01_07_V2”) by adding a question on age. We have completed surveys with about 140 participants across the three age/sex strata. Using the same question as in the Contact Sheet, we will re-contact these participants to collect information on their age. Upon approval, we will administer this survey over the phone to about 250-280 men and women age-eligible for screening, so as to have about 50-60 women 21-49 years (cervical cancer), 100-110 men 50-75 (CR and prostate cancers) and 100-110 women (breast, CR, and cervical cancers). The sample size for women aged 21-49 eligible for the survey with a focus on questions only on cervical cancer is lower in light of the fact that the survey of women aged 50-75 will include questions regarding cancer of the cervix, besides cancers of the breast and CR. We will use validated questions from the Behavioral Risk Factor Surveillance Survey, the National Health Interview Survey (Cancer Supplement), our previous research, and new questions based on findings from the focus group discussions. We will setup the

survey on REDCap. Before starting the survey we will read the consent letter requiring no documentation of written consent (see “Consent_Survey_Men50-75_2020_06_22_V1”, “Consent_Survey_Women21-49_2020_06_22_V1”, and “Consent_Survey_Women50-75_2020_06_22_V1”). The survey will average about 20 minutes to complete for men 50-75 years and women 21-49 years, and 40 minutes to complete for women 50-75 years. Men 50-75 years and women 21-49 years will receive a \$25 merchandise card, and women 50-75 years will receive a \$50 merchandise card in appreciation of their time. We will mail the merchandise cards to the participants (see “ThankYouNote_2020_06_22_V1”). If the participants request, we will mail the Consent Letter along with the merchandise card.

Aim 5: Integrate data to better understand cancer prevention and control challenges for the Zuni people:

- a. Ascertain cancer burden, risk factors, and screening rates among the Zuni people.
- b. Synthesize data collected as part of Aim 3b on resources available in the community, IHS Zuni Comprehensive Health Center, and at UNM CCC that can address the Advisory Panel-identified cancer prevention and control priorities.
- c. Synthesize data collected as part of the qualitative and quantitative research (Aims 3a and 4).

We will integrate data from three sources (i.e., state/national databases [Aim 5a], assessment of cancer prevention and screening resources available [Aim 5b], and qualitative research [Aim 5c]) to better understand cancer prevention and control needs for the Zuni people. Prior to compiling any data, we will consult with the Advisory Panel regarding its preferences on the types, extent, and details of data to help prioritize Zuni-specific cancer control needs. First (Aim 5a), we will have [name] (Director, NMTR) analyze and present to the community collaborative Zuni-specific and comparative data on cancer epidemiology. These data will include cancer incidence, mortality, 5-year survival, stage-at-diagnosis, and trends over time for Zuni and also compared with other AIs and racial/ ethnic groups in NM. We will also compile and present data on risk factor and rates of screening for screen-detectable cancers obtained from the Albuquerque Area IHS Government Performance and Results Act data, NM Indicator-Based Information System and the Behavioral Risk Factor Surveillance System. We will note limitations of these databases in accurately collecting and reporting data about tribal communities. Second (Aim 5b), we will synthesize data collected as part of Aim 3b on resources available in Zuni, IHS Zuni Comprehensive Health Center, and at UNM CCC to address the Advisory Panel-identified cancer prevention and control priorities. These resources will include, but not be limited to, availability of and capacity for: screening services; cancer risk reduction health and wellness programs; trained medical and non-medical personnel for cancer prevention and control activities; follow-up diagnostic, treatment and management facilities; and IT and database management resources. Third (Aim 5c), we will synthesize and integrate qualitative and quantitative research data collected as part of Aims 3a and 4. These data will provide insights about Zuni residents’ perspectives on cancers of the breast, CR, and cervix. Specifically, the qualitative data will shed light in the following areas: 1) knowledge about the respective cancer, 2) belief and attitudes (cultural, social, behavioral) regarding preventive behaviors in general, and cancer prevention in particular, 3) individual and social factors that facilitate and impede reducing risk and promoting better health, 4) factors that pose barriers and facilitate obtaining screening exam, 5) social determinants of health, and 6) strategies that can enhance screening behavior.

Integration of data from these three sources will help better understand needs and challenges for Zuni-specific cancer prevention and control efforts. Coupled with this understanding, the granular data will be foundational in the prioritization of needs, and the development and implementation of tailored and targeted intervention trials.

Aim 6: Develop a cancer prevention and control research agenda for tribal communities in rural NM:

- a. Develop a Zuni-specific comprehensive plan for research and evidence-based interventions in cancer prevention and control.
- b. Design a model, based on the lessons learned, for a collaborative cancer prevention and control research agenda for tribal communities across rural NM.

Aim 6a: The TAP will review the multi-component data analyzed as part of Aims 4 and 5 to set priorities for the Zuni-specific cancer prevention and control research agenda. The TAP will set priorities based on defining cancers that have the biggest impact on the Zuni community. Since this will be a participatory process, it is difficult to *a priori* identify algorithms that we will use to define and set the priorities. The priorities could be set based on cancer(s) with a high incidence but low mortality above or below cancer(s) with low incidence but high mortality; changing trends in incidence, mortality, and 5-year survival; treatment costs; length of stay in a hospital; established evidence-based primary or secondary prevention and control strategies recommended by The Community Guide and USPSTF; evidence for preventing cancer(s) (i.e., modifiable risk factors); and availability of community and healthcare resources.

Aim 6b: We will assess challenges and facilitators to developing the Zuni-specific cancer prevention and control research agenda. The assessments will document: (1) aspects of developing the collaborative (i.e., collaboration between entities with different institutional missions, representative participation, trust building, engagement). (2) development and sustenance of research capacity through focused and time-limited training and education. (3) compilation, analysis, presentation, and critical appraisal of data on cancer control needs that may be limited by small sample sizes. (4) defining and setting cancer prevention and control research priorities within the context of uncertainties regarding availability of and access to adequate resources in rural NM. Based on the lessons learned from this assessment, we will develop a model for translating and sustaining a cancer prevention and control research agenda across other AI tribes in rural NM. We will develop plans for cancer control research in collaboration with 11 additional tribal communities in the IHS Albuquerque Area that are situated in RUCA categories 7-9.

Aim 7: Using participatory approaches by engaging the TAP, finalize multilevel/ multicomponent intervention strategies to increase provider delivery of, community access to, and community demand for screening for the screen-detectable cancers.

